5.1.4 SAFETY FOLLOWUP

An SFU for all participants, including patients prematurely withdrawn from treatment, will be conducted 6 weeks after the EOT visit. This visit will include:

- Physical examination
- Complete neurological examination
- Anthropometrics
- Vital signs
- Laboratory monitoring. Participants will be contacted with results requiring intervention
- Pregnancy test: a serum pregnancy test will be taken for applicable participants.
- Concomitant medications
- Seizure Frequency
- Review of Adverse Events
- Review of seizure frequency
- ECG: may be collected within 1 week prior to study visit.

5.2 OUTCOMES ASSESSMENTS

5.2.1 SAFETY AND TOLERABILITY ASSESSMENT

The safety and tolerability of VOR at a dose of 230 mg/m²/day in a pediatric population with medically intractable epilepsy will be assessed via incidence of AEs and SAEs, as well as discontinuations due to intolerable AEs, identified through Safety Monitoring Activities (See [Section 5.3](#)).

It is anticipated that the tolerability of VOR in a medically resistant population of pediatric patients with epilepsy will be similar to that seen with currently prescribed AED therapies. Namely, the incidence rate for overall AEs is anticipated to be up to 55%; incidence of SAEs to be no more than 10%; no deaths are expected in the course of the trial; and discontinuation rate due to intolerable AEs is expected to be up to 30%.

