1.1 BACKGROUND

1.1.1. DISEASE

Epilepsy is defined as the occurrence of two or more unprovoked seizures, caused by abnormal, excessive discharge of neurons, usually accompanied by behavioral or sensorimotor manifestations¹. An estimated 15,500 new patients are diagnosed with epilepsy each year in North America alone².

Several therapies are available for the treatment of seizures, including over 10 pharmaceutical agents, as well as surgical, neurostimulation, diet, and immunomodulatory interventions, with the goals of complete seizure remission, minimal or no adverse effects (AEs), and best quality of life (QoL)^{3, 4}. Despite these numerous available therapies, attainment of treatment goals continues to be elusive. Approximately 85% of patients are prescribed an anti-epileptic drug (AED) within one year of the first unprovoked seizure⁵; of those only 30 - 50% achieve seizure freedom^{5, 6}, and 30–60% experience drug-related AEs⁷. About a third have medically intractable epilepsy^{5, 8}, which is defined by the International League Against Epilepsy (ILAE) 2010 task force as “failure of adequate trials of two tolerated, appropriately chosen and used antiepileptic drug schedules (whether as monotherapies or in combination) to achieve sustained seizure freedom”⁹.

Uncontrolled seizures in children can impose a deleterious impact on development, increase the risk of medical complications and injuries, contribute to poor QoL¹⁰, and significantly increase mortality rate (1.59% per year)^{10, 11}. Almost half of the children with medically intractable epilepsy may evolve some intellectual dysfunction or decline in cognitive function over the years¹²⁻¹⁴. Children with epilepsy are at particular risk for impaired QoL and psychological problems, and are among those with the poorest QoL and worst psychological adjustment during infancy and adolescence, compared to other chronic conditions not involving central nervous system conditions^{15, 16}. The risk of death in children with epilepsy is several-fold higher over the subsequent 10-20 years of life¹⁷; and lack of seizure freedom is the greatest risk factor for premature death in this population¹⁸. Furthermore, the associated medical care costs of sub-optimal control of seizures is exorbitant: while the direct and indirect costs of epilepsy are estimated to be \$9.6 billion (US data)¹⁹⁻²¹, the health care costs of patients with uncontrolled seizures or AEs are estimated to be twice as high²².

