3.1 OVERVIEW OF STUDY DESIGN AND DOSING REGIMEN

The study will consist of a single centre, open-label Phase 2A/B pilot study evaluating the safety, tolerability, and efficacy, of VOR in a pediatric population with medically intractable epilepsy. Participants will be administered 230 mg/m²/day of VOR in addition to standard of care anti-seizure medication for a duration of 6 weeks.

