4.7 CRITERIA FOR PREMATURE WITHDRAWAL

Participants have the right to refuse treatment or completely withdraw from the study at any time for any reason. The investigator also has the right to discontinue treatment and withdraw participants from the study treatment in the event of intercurrent illness, AE, treatment failure, protocol violations, administrative reasons, or other reasons deemed necessary by the investigator.

Participants with significant drug compliance issues or safety monitoring compliance issues, not related to AEs will be withdrawn from the treatment phase of the study by the investigator and an EOT visit as well as an SFU visit will be attempted to be performed in all cases.

If the participant withdraws from study treatment only, they will undergo an EOT visit and SFU visit. If the reason for removal of a participant from the study is an AE or an abnormal laboratory test result, the principal specific event or test will be recorded in the study record. If the participant explicitly withdraws consent for additional follow-up, the participant will be asked to undergo a phone SFU visit at the absolute minimum. In addition, all efforts will be made to complete and report the observations prior to withdrawal as thoroughly as possible. A complete final evaluation at the time of the participant's withdrawal should be made with an explanation of why the participant is withdrawing from the study. In the event that a participant is lost to follow up, the last assumed day of medication will be the last day for which number of doses was provided. An attempt will be made to contact participants, via provided phone, email, and registered letter to the address provided. All attempts to contact will be recorded in the study record. In the event that all attempts for contact fail, a chart review and review of NetCare will done at 6 weeks following the last assumed day of medication.

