5.3 SAFETY MONITORING

5.3.1 ADVERSE EVENTS

AEs (serious and non-serious) reported by the participant or observed by the investigator will be collected throughout the study. At each visit, the investigator will ask the participant if any untoward medical event occurred since the last visit. For each event, the date of onset and date of resolution, intensity, relationship to study medication, outcome and treatments administered for the event will be recorded in the study record.

AEs will include any symptom, sign, illness or experience, or clinically relevant lab abnormality, regardless of causality, which develops or worsens in severity during the course of the study. An SAE will comprise of any AE, occurring at any dose, regardless of causality that was either life-threatening, requires inpatient hospitalization or prolonging an existing hospitalization, or is determined as an important medical event by the treating physician, or results in death.

All AEs will be reported as stipulated in [Section 7.1](#). SAEs will be reported to the research ethics board (REB) and to Health Canada.

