6.2.3 DOSE INTERRUPTIONS

If a dose is missed, it should be taken as soon as possible. If the participant does not remember until it is nearly time for the next dose, the participant should skip the missed dose and go back to the regular schedule. A double dose of should not be taken.

There will be no temporary interruptions of study medication due to safety reasons. If study medication is stopped due to safety reason, there will be no re-challenge.

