7.1.3 TREATMENT AND FOLLOW UP OF AEs

AEs will be followed up until they have returned to baseline status or stabilized. Details of follow up will be recorded in the study record including if return to baseline status or stabilization cannot be achieved.

In the event of medically significant unexplained abnormal laboratory test values, the tests will be repeated and followed up until they have returned to the normal range or the baseline value and/or an adequate explanation of the abnormality is found. All details will be included in the study record.

If the study drug is discontinued due to an AE or a laboratory abnormality, the study medication will not be reinstated. If the investigator decides to discontinue study drug treatment, the rationale for their decision will be provided in the AE comment/SAE narrative field of the study record.

Study drug will be discontinued in the presence of an SAE that is deemed to be related or possibly related. Thromboembolic events or any event which a participant finds intolerable, which cannot be mitigated with therapy, will be cause for VOR discontinuation. Participants experiencing a $\geq 50\%$ increase in seizure frequency, as compared to baseline at any time during the treatment period will be discontinued from study medication. Additionally, participants presenting with status epilepticus at any time during the treatment period will be discontinued from study medication.

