7.2.3. PREGNANCY

Pregnancies occurring in female participants exposed to the study medication, or partners of male participants exposed to the study medication, will be reported to the REB. Female participants, or partners of male participants will be instructed to notify the investigator as soon as possible. Female participants will be instructed to discontinue taking the study medication immediately. Study medication will be permanently discontinued in female participants and an EOT and SFU visit will be conducted as per protocol. Participants or partners of male participants will be followed until the conclusion of pregnancy. Pregnancies occurring up to 90 days after the completion of the study medication will be followed in the same manner.

The investigator will counsel and discuss with the participant/partner of participant the risks of continuing with the pregnancy and the possible effects of early exposure to study medication on the fetus.

Where a SAE occurs in the pregnant female participant, the SAE must be collected separately, regardless of whether it is pregnancy related or not.

SECTION 8: STATISTICAL CONSIDERATION AND ANALYTICAL PLAN

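### Every prespecified stopping rule acts on one child; nothing in the plan pauses new first doses or prompts a cumulative review after a death or several related SAEs

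*Combined protocol and SAP*

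**What the plan says.** Section 3.1: "The study will consist of a single centre, open-label Phase 2A/B pilot study". Section 3.3 sets 12 children, and section 8.2.1 bases that number on feasibility and cost. Section 1.1.4 states that vorinostat's tolerability in epilepsy cannot be given because it has not been tested there. Section 1.1.4.3 accepts that serious hematologic events remain possible.

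Section 5.2.1 forecasts the "incidence of SAEs to be no more than 10%; no deaths are expected in the course of the trial". SAEs are counted whatever their cause (5.3.1: "An SAE will comprise of any AE, occurring at any dose, regardless of causality").

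The stopping rules are:
- 4.7: "The investigator also has the right to discontinue treatment and withdraw participants from the study treatment", plus withdrawal for poor compliance.
- 6.2.3: "If study medication is stopped due to safety reason, there will be no re-challenge".
- 7.1.3: "Study drug will be discontinued in the presence of an SAE that is deemed to be related or possibly related". The same section stops drug for thromboembolism, intolerable events, status epilepticus and a seizure increase of 50% or more.
- 7.1.3.1: thromboembolism again.
- 7.2.3: "Study medication will be permanently discontinued in female participants".

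SAEs are entered within 24 hours of awareness and notified to the REB and Health Canada (5.3.1, 7.2.2). Section 8.2.2.1 tabulates AE rates at fixed times with no decision rule. Section 10 provides for consent revision if new safety information changes the risk/benefit assessment.

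**The concern.** Each rule answers whether this child should stop. None answers whether the next child should start. The forecasts in 5.2.1 are the only study-level safety figures, and exceeding them has no consequence. Section 10 says what follows once the risk/benefit assessment has changed, but nothing triggers that assessment. No section describes a monitoring committee, an interim or cumulative safety review, or staggered first doses.

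Safety is the primary objective, and this is, to the sponsor's knowledge, the first trial of the drug in children with intractable epilepsy. Followed as written, the protocol would allow first doses to continue after a death or a cluster of related SAEs. A hold would depend on the investigator's judgement, or on an outside body reacting to individual reports.

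**Working it through.** **Is there a study-level rule?** The five sections above each name a participant, or the study drug in a participant, as the object of the action. Sections 5.3.1 and 7.2.2 deal with single-event reporting, 8.2.2.1 with tabulation, and Section 10 with consent. There is no stated boundary to reproduce, and the prespecified chance of a hold is zero at any SAE rate.

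**Inputs.** From the documents: N = 12; the 10% all-cause SAE forecast; six weeks on drug and six of follow-up; and section 1.1.1's statement that uncontrolled seizures "significantly increase mortality rate (1.59% per year"). Assumed, because the documents do not give them: true related-SAE rates, accrual pace, onset timing, and lag from onset to hold.

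**How often would an SAE trigger be reached?** Let X be the number of children with a related SAE, binomial(12, p).
- At p = 0.10 the expected count is 1.2. P(X≥1) = 71.8% and P(X≥2) = 34.1%, so a trigger at one or two children would fire too readily.
- P(X≥3) at p = 0.10 is 1 − (0.9^12 + 12×0.1×0.9^11 + 66×0.1²×0.9^10) = 1 − (0.282 + 0.377 + 0.230) = 11.1%.
- P(X≥3) at p = 0.05 / 0.20 / 0.30 / 0.40 is 2.0 / 44.2 / 74.7 / 91.7%.
- P(X≥4) at p = 0.05 / 0.10 is 0.2 / 2.6%.

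The 10% forecast covers all SAEs, so the related rate should be no higher than that if the forecast is right.

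**Death trigger.** If 1.59% per year applied to 12 children over 12 weeks: 1 − exp(−0.0159 × 144/52.18) = 4.3%. With weekly starts, 66 child-weeks (0+1+…+11) accrue before the last start: 1 − exp(−0.0159 × 66/52.18) = 2.0%.

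**Either trigger, if independent.** At p = 0.10: 1 − (1 − 0.111)(1 − 0.043) = 14.9%. At p = 0.05: 1 − (1 − 0.020)(1 − 0.043) = 6.2%.

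**How often would a hold spare a child?** These are simulations of 400,000 trials per cell. A hold takes effect at the third onset plus the lag, and onset is uniform over six weeks from each child's first dose unless stated. The entries are P(at least one child not dosed).

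| Starts | Lag | p=0.20 | p=0.30 | p=0.40 |
|---|---|---|---|---|
| Weekly | none | 23% | 49% | 72% |
| Weekly | 2 weeks | 13% | 31% | 51% |
| Weekly, onset over 12 weeks | none | 9% | 22% | 38% |
| Two per week | none | 9% | 22% | 38% |
| Two per week | 2 weeks | 1% | 2% | 5% |
| One per 2 weeks | none | 32% | 62% | 83% |

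With weekly starts and no lag, mean children dosed is 11.3 / 10.4 / 9.3 of 12; with a two-week lag it is 11.7 / 11.3 / 10.6. At p = 0.20 with weekly starts and no lag, 0.232 of the 0.442 triggers come in time; the rest (0.210, about 48%) fire after the last child has started. In the same no-lag weekly case a dose is withheld in about 5% of trials at p = 0.10 and 1% at p = 0.05.

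**The case against.** The case against is substantial, and most of it stands as a limit on size.

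- **Existing protection.** A related SAE already ends dosing in that child without re-challenge, laboratory tests run every two weeks on treatment, and the REB and Health Canada hear of SAEs. With 12 children at one open-label site, one team sees everything. This narrows the gap to a missing trigger and a missing documented decision. It does not close it: seeing events obliges nobody to stop and review them together, and the investigator also rates causality.
- **No error in the plan.** A reader might infer that 10% is a safety threshold the protocol fails to enforce. It is a forecast, and the protocol claims no study-level rule, so nothing is internally inconsistent.
- **Uncertain benefit.** A reader might infer that a hold would reliably keep children off the drug. The documents give no accrual pace, and zero lag is the most favourable case. AEs are asked about at visits two weeks apart, although 5.1.3 encourages earlier contact, and relatedness must then be judged. The table shows how quickly the benefit can disappear.
- **Unnecessary pauses.** The combined chance is about 15% at a 10% related rate, roughly one in seven, and the death trigger would also fire on a death unrelated to drug.
- **Ambiguous causality.** Section 7.1.1.2 allows only Yes or No, while 7.1.3 speaks of related or possibly related. A trigger must tie the two together.

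**Conclusion.** The gap is real and the improvement is worth making, with medium confidence. Any hold on new first doses after a death or several related SAEs currently rests on discretion.

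The assured gain is that a documented cumulative review takes place. Sparing children a first dose is a further gain that is likely only if accrual is slow. With one start every two weeks and a two-week lag, it still happens in about 26% of trials at a true rate of 20% and a little over three quarters at 40%.

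Two stronger readings are not supported. Three of 12 would not demonstrate an excess over 10%: its exact 95% interval runs from 5.5% to 57.2%. Nor does the 65% figure in 1.1.4.3, which counts Grade 4 events as SAEs, predict the rate here. It comes from heavily pretreated oncology patients, mostly on combinations, and the protocol itself doubts that it transfers.

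The pause probabilities assume independent events; the 4% death figure also assumes that the quoted mortality applies to these children.

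**What to change.** Add to 5.2.1 and 7.2 a temporary hold on new first doses, with a cumulative safety summary to the CHREB and Health Canada and a documented decision to resume, amend or close, at either:

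- (a) any death within the AE reporting period; or
- (b) a third child with an SAE leading to discontinuation under 7.1.3 as related or possibly related, defined as rated Yes under 7.1.1.2.

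Children already on drug stay under 7.1.3. The sponsor may prefer another count but should state its pause probability. A fourth-child trigger is reached in 2.6% of trials at a 10% rate; with weekly starts and no lag it spares a child in about 7% at a true rate of 20% and 46% at 40%.

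The cost is a short amendment and a running count kept by existing staff, reported to bodies that already receive the SAEs. No new committee is needed. The downside to state openly is an unnecessary temporary pause, at the combined probabilities shown above.

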5.2.2 EFFICACY ASSESSMENTS

5.2.2.1 PRIMARY EFFICACY ASSESSMENTS

Treatment response will be determined by the proportion of participants who have at least at 50% reduction rate of seizures.

5.3 SAFETY MONITORING

5.3.1 ADVERSE EVENTS

AEs (serious and non-serious) reported by the participant or observed by the investigator will be collected throughout the study. At each visit, the investigator will ask the participant if any untoward medical event occurred since the last visit. For each event, the date of onset and date of resolution, intensity, relationship to study medication, outcome and treatments administered for the event will be recorded in the study record.

AEs will include any symptom, sign, illness or experience, or clinically relevant lab abnormality, regardless of causality, which develops or worsens in severity during the course of the study. An SAE will comprise of any AE, occurring at any dose, regardless of causality that was either life-threatening, requires inpatient hospitalization or prolonging an existing hospitalization, or is determined as an important medical event by the treating physician, or results in death.

All AEs will be reported as stipulated in [Section 7.1](#). SAEs will be reported to the research ethics board (REB) and to Health Canada.

5.3.2 SAFETY MONITORING

All safety monitoring will be performed as summarized in [Table 5: Schedule of events](#).

5.3.2.1 VITAL SIGNS

Seated blood pressure and pulse will be recorded after at least a 5-minute rest. Two measurements should be made for each blood pressure measurement and the average derived.

5.3.2.2 ANTHROPOMETRICS

Body weight and height will be measured at each study visit.

5.3.2.3 DIRECTED PHYSICAL EXAM

The directed physical examination will include a general physical examination and neurological examination. Special attention will be paid to the signs and symptoms reported with VOR. Any clinically significant abnormalities persisting at the end of the study will be followed by the investigator until resolution or until achievement of a clinically stable endpoint.

5.3.2.4 LABORATORY BLOOD SAMPLES

All blood samples will be taken and processed by the Calgary Lab Services.

Hematology

Blood samples will be obtained to conduct a complete blood count, according to the schedule summarized in [Table 5: Schedule of events](#).

Coagulation

Blood samples will be obtained to assess coagulation (PTT/INR)

Serum Chemistry

Blood samples will be obtained to assess the following, according to the schedule summarized in [Table 5: Schedule of events](#):

- renal function (serum creatinine and blood urea nitrogen)
- hepatic function (bilirubin, ALT, AST, and albumin)
- electrolyte monitoring, including: sodium, potassium, chloride, magnesium, and calcium
- blood glucose
- lactate dehydrogenase

5.3.2.5 PREGNANCY TEST

Serum β -HCG levels test will be obtained for heterosexually active women of childbearing potential, according to the schedule summarized in [Table 5: Schedule of events](#).

A urine pregnancy test will be done in office at the enrollment visit for applicable participants.

5.3.2.6 ECG

ECG will be recorded a total of 3 times, according to the schedule summarized in [Table 5: Schedule of events](#).

SECTION 6: INVESTIGATIONAL MEDICINAL PRODUCT

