- Seizure Frequency: Participants will be asked to provide their seizure tracker information since the last study visit. Participants' seizure types and how to accurately record seizure frequency will be reviewed by the investigator at each study visit. If participants commence to exhibit new seizure types, they will be asked to collect the seizure frequency of the new seizure type.
- ECG: an ECG will be conducted on Visit 3. The ECG may be collected within 1 week prior to study visit depending on appointment availability at the ECG lab.

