8.2.2 ANALYSIS

8.2.2.1. SAFETY & TOLERABILITY ANALYSIS

Safety and tolerability will be assessed by calculating the incidence rate of AEs per number of drug days from the time medication is started through to the completion of the SFU (or 42 days following the last dose of study medication). This will be done for the following time points: 14 days following drug initiation; 30 days following drug initiation; 42 days following drug initiation; and 42 days following drug discontinuation. AEs will be further stratified by mild/moderate AEs, severe AEs, and SAEs, as well as project specific AEs (thromboembolism, hyperglycemia, gastrointestinal disturbances, dehydration, hematologic disturbances, QT/QTc prolongation).

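### QT/QTc prolongation is to be reported per drug-day up to day 42, but the only scheduled on-drug ECG is around week 2, so the later rates mainly reflect the ECG schedule

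*Combined protocol and SAP*

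**What the plan says.** Section 8.2.2.1 assesses safety by "calculating the incidence rate of AEs per number of drug days from the time medication is started". The stated time points are "14 days following drug initiation; 30 days following drug initiation; 42 days following drug initiation; and 42 days following drug discontinuation". Events are then stratified by severity and by project-specific type, and the list of types ends with "hematologic disturbances, QT/QTc prolongation".

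Section 5.3.2.6 says "ECG will be recorded a total of 3 times". Table 5 marks them at V1 (screening), V3 (week 2) and SFU (week 12), with none at enrollment, V4 or EOT. The prose agrees. Section 5.1.3 says "an ECG will be conducted on Visit 3" and adds: "The ECG may be collected within 1 week prior to study visit depending on appointment availability at the ECG lab". Section 5.1.4 gives the follow-up ECG the same allowance: "ECG: may be collected within 1 week prior to study visit".

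Two provisions allow unscheduled ECGs. Section 4.5.2 recommends one for a participant taking a QT-prolonging drug when the next protocol ECG is more than a week away. Section 7.1.3.1 permits additional ECG monitoring and asks participants to report symptoms such as syncope or palpitations.

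**The concern.** QTc prolongation is found by ECG. Drug-days after the Visit 3 ECG still enter the denominator, but none of them can produce a finding from a scheduled ECG. The day-30 and day-42 figures therefore combine a numerator that is essentially fixed around week 2 with a denominator that keeps growing.

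This stratum differs from the others on the project-specific list. Blood counts and glucose are measured at weeks 2, 4 and 6, and gastrointestinal events and thromboembolism present clinically. Section 7.1.3.1 notes that torsade de pointes may be without symptoms, so symptom reports cannot be relied on to fill the gap.

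Safety is the primary endpoint, and QT/QTc prolongation is a risk that the protocol singles out. A rate that is lower at day 42 than at day 14, or a zero over several hundred drug-days, could be read as reassurance about weeks 3 to 6, when no routine ECG was done.

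**Working it through.** **Inputs.** 12 participants (3.3); 42 days of treatment (3.1.2); ECGs at V1, V3 and SFU, Visit 3 at day 14 ± 2 (Table 5); ECG allowed up to 7 days before the visit (5.1.3); discontinuation for adverse events expected up to 30% (5.2.1).

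**1. ECG count.** Table 5 has marks at V1, V3 and SFU, which gives 3 and reproduces the figure in 5.3.2.6. Only one of these, V3, is on drug.

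**2. Timing of the on-drug ECG.** Visit 3 falls on days 12 to 16. The earliest ECG is 12 − 7 = day 5 and the latest is day 16. Drug-days after it: 42 − 16 = 26 to 42 − 5 = 37.

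**3. Base case.** Cumulative rate at day d = events to day d ÷ drug-days to day d. With full dosing, drug-days are 12 × 14 = 168, 12 × 30 = 360 and 12 × 42 = 504. One event found by day 14 and none later gives, per 1000 drug-days:
- day 14: 1000/168 = 5.95
- day 30: 1000/360 = 2.78, a fall of 1 − 14/30 = 53.3%
- day 42: 1000/504 = 1.98, a fall of 1 − 14/42 = 66.7%

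The percentages do not depend on the number of events, provided that there is at least one.

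**4. Other readings.**

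| Assumption changed | Arithmetic | Change from day 14 to day 42 |
|---|---|---|
| 30% discontinue, all at day 14 | 12 × (0.7 × 42 + 0.3 × 14) = 403.2; 1 − 168/403.2 | falls 58.3% |
| 30% discontinue, evenly over 42 days | 159.6 drug-days to day 14, 428.4 to day 42; 1 − 159.6/428.4 | falls 62.7% |
| Only the one QT case stops, at day 14 | 11 × 42 + 14 = 476; 1 − 168/476 | falls 64.7% |
| One further event from an unscheduled ECG before day 42 | 1 − (2/42)/(1/14) | falls 33.3% |
| ECG done on day 15 or 16 | 0 at day 14, 2.78 at day 30, 1.98 at day 42 | rises, then falls 1 − 30/42 = 28.6% from day 30 |
| Separate intervals, ECGs by day 14 | no scheduled ECG in days 15–30 or 31–42 | falls 100% |

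**5. No events.** The table shows 0 over up to 504 drug-days. The scheduled on-drug evidence is one ECG per child, so at most 0 of 12.

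**6. Follow-up time point.** The follow-up ECG is off drug. If drug-days stop at the last dose, a finding there adds to the numerator and nothing to the denominator. One on-drug event plus one at follow-up gives 2000/504 = 3.97 per 1000, against 1.98 at day 42.

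**The case against.** A reader might infer that the rate will fall by two thirds as a fixed result of the schedule. The documents do not support that. The figure needs at least one event, a cumulative rate, every ECG by day 14, full dosing to day 42 and no later QT finding. Section 8.2.2.1 does not say whether rates are cumulative or by interval, and it does not state outright that every stratum is tabulated at every time point, though that is the natural reading. The visit window allows an ECG on day 15 or 16, which reverses the direction between day 14 and day 30.

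A reader might also infer that no QT finding is possible in weeks 3 to 6. That goes too far as well. Adverse events are collected throughout, unscheduled visits are allowed, and sections 4.5.2 and 7.1.3.1 provide for extra ECGs. These routes are optional and depend on symptoms or co-medication. They narrow the gap without closing it, and they give no common denominator.

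The illustrated drop may never appear. The protocol's own pediatric review has 1 prolonged QTc in 110 patients. At face value, the chance of any case among 12 is 1 − (109/110)^12, about 10%, and the protocol itself warns against extrapolating from oncology. This is a 12-patient descriptive pilot with no hypothesis test. That limits the weight of the point but does not remove it, because a bare zero over 504 drug-days is also open to misreading.

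Finally, reporting the number prolonged might seem to require a new threshold; the only QTc figure in the plan is the eligibility limit of 450 msec. The objection is met by using QT/QTc prolongation as it is recorded as an adverse event.

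**Conclusion.** The concern holds. Between 26 and 37 of 42 drug-days per fully dosed child follow the only scheduled on-drug ECG, so the QT/QTc rates at days 30 and 42 mainly describe when ECGs were done.

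The size is conditional. The cumulative rate falls by up to two thirds with full dosing, all ECGs by day 14, at least one event and no later finding. It falls by about 58–63% if 30% discontinue. It moves from zero up and then down if the ECG falls on day 15 or 16. The mismatch between denominator and measurement is present in every reading; only its size or direction changes. At the fourth time point an off-drug finding would be divided by on-drug days, which can double the rate.

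This is a fault in how one safety stratum is reported. It does not affect a power calculation or a formal test, since the plan has neither. It is worth correcting because safety is the primary endpoint and the change costs little.

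**What to change.** In section 8.2.2.1:
- Report QT/QTc prolongation, as recorded as an adverse event under the protocol, as the number of participants with the event over the number with an ECG, separately for Visit 3 and the follow-up visit.
- Mark days 30 and 42 'no scheduled ECG' for this stratum.
- List findings from unscheduled ECGs separately.
- If a per-drug-day rate is kept, footnote the number of participants with an ECG at each time point, including follow-up.

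Change from screening QTc is optional. Note that the screening value may come from a clinically indicated ECG done up to a month before screening (5.1.1).

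The sponsor should reconcile the ECG schedule with the reporting time points. The reporting change itself needs no added procedure and no new QTc threshold.

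The cost is wording in the analysis section. The downsides are that one metric no longer serves every stratum, and that the report shows openly that weeks 3 to 6 had no routine ECG.
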